STUDY TITLE	Dräger Antigen Test SARS-CoV-2 Clinical Performance Study
SPONSOR	Drägerwerk AG & Co. KGaA, Lübeck, Germany
PROJECT LEAD	[name]
NUMBER OF SITE	20-GER-01
RATIONALE	The Dräger Antigen Test SARS-CoV-2 is a rapid lateral flow immunoassay for the qualitative detection of SARS-CoV-2 nucleoprotein directly from minimally invasive nasal swabs directly at the point of care. The coronavirus SARS-CoV-2 can cause a mild to severe respiratory illness, i.e. COVID-19, and has spread globally. Already existing rapid tests are mostly based on invasive nasopharyngeal sampling and involve cumbersome sample extraction procedures requiring well trained users. Given the simple and less invasive sampling methodology of the Dräger rapid test, it is worthwhile to execute the proposed study as no harm is expected for the participants and a rapid and easy test is to be gained.
STUDY DESIGN	Prospective, monocentric, clinical performance evaluation study for an IVD
PRIMARY OBJECTIVE	Determine general sensitivity and specificity of the Dräger Antigen Test SARS-CoV-2 in symptomatic participants in comparison to the reference method RT-PCR (at a threshold of $\geq 10^6$ RNA copies/mL for positive PCR results)
SECONDARY OBJECTIVE(S)	
Sensitivity and specificity of the test under evaluation in relation to the ct value of the reference testSensitivity and specificity of the test under evaluation in relation to the time since symptom onsetSpecificity of the test under evaluation in at least 100 asymptomatic participantsFrequency of nosebleed or unbearable pain during or immediately after specimen collection
INTERVENTIONS	No therapeutical interventions, no randomization
NUMBER OF PARTICIPANTS	approximately 850
PROCEDURE	Female and male adults with a pre-existing need for SARS-CoV-2 testing undergo screening for study participation suitability at the study site. Two separate sets of participants are included: persons with COVID-19 symptoms (symptomatic group) and persons who might have been exposed to SARS-CoV-2 but show no symptoms (asymptomatic group). Participants are required to meet all inclusion criteria and none of the exclusion criteria. All participants are tested with the Dräger Antigen Test SARS-CoV-2. RT-PCR results for pharyngeal swabs from the same participants serve as reference. This test is not initiated on the Sponsor's behalf; rather the Sponsor asks the participants to allow the PI to share pseudonymized PCR results as reference to compare to the results generated by the investigational product. All test results are collected for performance analysis of the Dräger Antigen Test SARS-CoV-2. Criteria for early study termination have been defined to avoid unnecessary strain for participants.

PARTICIPANT SELECTION CRITERIA	Inclusion		Exclusion					
	General	
 • ≥ 18 y old • Written informed consent (ability & execution) • Pre-existing need for SARS-CoV-2 testing, i.e. 
 ◦ COVID-19 symptoms ◦ Known or suspected exposure to SARS-CoV-2 ◦ Screening 	
 • < 18 y old • Pregnant or breast-feeding women • Unable to provide informed consent • Bleeding disorder • Application of nasal spray prior to testing on the day of testing • Involuntarily held in an institution • Hospitalization/inpatient 					
	Specific	
 
 Asymptomatic	 
 • Asymptomatic during the previous 14 days 	 
 • COVID-19 symptoms during the previous 14 days 	
 
 Symptomatic	 
 • COVID-19 symptom(s) present on the day of testing • Symptoms started 0-7 days prior to testing day 	 
 • Symptom(s) started more than 7 days prior to testing day 	
 
	Asymptomatic	
 • Asymptomatic during the previous 14 days 	
 • COVID-19 symptoms during the previous 14 days 	Symptomatic	
 • COVID-19 symptom(s) present on the day of testing • Symptoms started 0-7 days prior to testing day 	
 • Symptom(s) started more than 7 days prior to testing day
Asymptomatic	
 • Asymptomatic during the previous 14 days 	
 • COVID-19 symptoms during the previous 14 days 						
Symptomatic	
 • COVID-19 symptom(s) present on the day of testing • Symptoms started 0-7 days prior to testing day 	
 • Symptom(s) started more than 7 days prior to testing day 						
PRODUCT UNDER INVESTIGATION	
Dräger Antigen Test SARS-CoV-2
 
The investigational product is comprised of a sample collector and a test cassette. The sample collector retrieves the specimen from the anterior nose, while the test cassette analyzes the sample for the presence of SARS-CoV-2 nucleoprotein.
							
COMPARATOR	
RT-PCR specific for coronavirus SARS-CoV-2
 
Pharyngeal swabs are collected using the Cobas PCR Media Uni Swab Sample Kit (Roche). Samples are analyzed using the PCR-Kit Cobas SARS-CoV-2 (Roche). For scoring the PCR result negative or positive, a cycle threshold (ct) value is used. Unless otherwise indicated, this study scores a PCR result with a viral concentration of $\geq 10^6$ RNA copies/mL as positive and $< 10^6$ copies/mL as negative. For data analysis, the corresponding ct value is provided based on PCR system calibration.
							
DURATION OF PARTICIPATION AND STUDY DURATION								
SCREENING	Study staff identifies eligible patients over the course of a month. If needed, this period can be extended.							
TREATMENT	Specimens for the Dräger test and comparator method are collected during the same one patient visit.							
FOLLOW-UP	None needed.							
OVERALL DURATION	January – March 2021, active phase 1 month							

1. INTRODUCTION

Coronaviruses are a large family of viruses which may cause illness in animals or humans (Masters, 2006; Weiss & Leibowitz, 2011). SARS-CoV-2 is an enveloped, single-stranded RNA virus of the β genus (Hasöksüz et al., 2020). The virus can cause a mild to severe respiratory illness named COVID-19 and has spread globally.

Several rapid tests have been developed based on immunochemical detection of viral nucleoprotein. The advantage of faster time to result compared to PCR testing and therefore earlier initiation of contact tracing is a great added benefit of rapid antigen tests (van Beek et al., preprint). Most of these tests are executed at the point of care by experienced users and allow for detection of an infection with SARS-CoV-2 in patients within the first 5 to 7 days since symptom onset.

Examples of existing rapid antigen tests:

- BinaxNOW™ COVID-19 Ag CARD (Abbott):
<https://www.fda.gov/media/141570/download>
- Veritor™ System (Becton, Dickinson): <https://www.fda.gov/media/139755/download>
- Standard Q Covid-19 Ag Test (SD Biosensor): https://bestbion.com/wp-content/uploads/2020/07/bestbiondx_GA_standardq_COVID-19-IgM-IgG-Duo_Ag20200713.pdf
- Biocredit Covid-19 Ag Test (Biocredit): https://www.biovendor.com/file/13419/1-2020IFU_COVID-19%20Ag%20RapigenWatermarked.pdf?version=202005131414

The above-mentioned rapid tests are mostly based on an invasive nasopharyngeal sampling procedure and involve cumbersome sample extraction procedures requiring well-trained operators.

The Dräger Antigen Test SARS-CoV-2 is a rapid lateral flow immunoassay for the qualitative detection of SARS-CoV-2 nucleoprotein directly from less invasive nasal swabs, to be performed at the point of care. The test kit contains all components required to carry out a test detecting SARS-CoV-2 nucleoprotein.

Given the less invasive sampling procedure and the straight-forward, fast testing procedure of the Dräger Antigen Test SARS-CoV-2, it is worthwhile to execute the proposed study as there is no harm expected for participating patients (see p. 10 for details). This study is designed as a non-interventional study, i.e. none of the Dräger test results are used to justify any patient management decisions.

2. STUDY DESIGN

The study is designed as a prospective, monocentric, clinical performance evaluation study. It is designed to demonstrate suitability of the Dräger Antigen Test for SARS-CoV-2 nucleoprotein detection in clinical nasal specimens. Real-time reverse transcriptase polymerase chain reaction (RT-PCR, here also short PCR) on specimens collected by pharyngeal swabs serves as a reference method for all participants of this study. In fact, participants are recruited from people presenting themselves for SARS-CoV-2 testing (pharyngeal swab and PCR) at designated testing locations of the study site. Each participant must meet all inclusion criteria of the respective group (i.e. symptomatic or asymptomatic). For details on the reference method and scoring (cut-off) refer to 4.3 and 6.2 below.

The goal of the study is to compare Dräger test results to the corresponding PCR data for overall sensitivity and specificity. Assuming a 20% PCR positive rate at the study site (prevalence), a 90% Dräger test sensitivity as the expected sensitivity, allowing room for

dropouts, and ensuring inclusion of at least 100 asymptomatic cases approx. 850 participants have to be enrolled (for details see case number estimation in 6).

Dräger provides approximately 900 Dräger test kits for this study to allow for practice runs and error. Should more testing become necessary after review of the half-way point or the endpoint, plans are made accordingly. When 425 data pairs of Dräger test and PCR results are available, the study reaches its half-way point. All data relevant for overall sensitivity and specificity are analyzed, and a brief overview of results serves as a preliminary summary at this point of time. Data relevant for secondary objectives are analyzed at the end of the study.

If people agree to participate, study staff records participants' information such as symptoms and time since symptom onset. For each study participant, the specimen for RT-PCR is collected first, then the Dräger test specimen. The participants self-sample the specimens using the Dräger sample collector closely supervised and guided by a qualified operator. Should the participant be compromised in some way such that self-sampling is not an option, the operator may collect the sample. The time of specimen collection for each test is recorded in the case report form (CRF). The Dräger test result is read after 15 min to 20 min, while the specimen for PCR is stored for further processing at a later time. Ideally, resulting data points are normally distributed along the age, gender, number of days with symptoms, and cycle threshold (ct) value or viral concentration spectrum.

3. STUDY OBJECTIVES

3.1 Primary Objectives

The primary objective of this study is to determine the levels of sensitivity and specificity of the Dräger Antigen Test SARS-CoV-2 based on direct nasal samples collected with the dedicated sample collector from symptomatic individuals requiring SARS-CoV-2 testing. The Dräger test result is compared to the reference method, that is RT-PCR. This study scores a PCR result of $\geq 10^6$ RNA copies/mL (viral concentration) as positive (RKI, 2020a). The diagnostic laboratory analyzing the PCR samples for this study determines the corresponding cycle threshold (ct) value for their system.

3.2 Secondary Objectives

In addition to the primary objective the following secondary objectives are investigated:

Sensitivity and specificity (and CI for CL of 95%) of the Dräger Antigen Test SARS-CoV-2 are determined for

- both the symptomatic and asymptomatic groups,
- case groups sorted by ct value, and
- case groups sorted by days since symptom onset.

Goal is to explore the data and describe the relationship between the respective parameter and Dräger test performance.

The occurrence of lasting nosebleed or unbearable pain during or immediately after specimen collection is recorded for each participant. The frequency is monitored throughout the study. Its final value is presented in the study report.

4. STUDY PROCEDURE

4.1 Study Enrollment Procedures

Participants are presented for SARS-CoV-2 testing to medical staff. In order to determine whether a participant is eligible for this clinical study, candidates are asked to provide some information via questionnaire (see Case Report Form [CRF] for details) and consent to study participation. Participants are recruited from both symptomatic and asymptomatic people based on criteria detailed below.

4.2 Inclusion and Exclusion Criteria

If inclusion criteria are not met, the participant is excluded from the study.

Inclusion criteria of individuals

- Participants must require SARS-CoV-2 testing for the following reasons:
 - COVID-19 symptoms (Fever, cough and/or sore throat, fatigue/ general feeling of weakness, loss of sense of smell and/or taste, shortness of breath, muscle stiffness/ body aches, head cold/ running nose, etc.) on the day of testing, or
 - Known or suspected exposure to SARS-CoV-2 (contact persons etc.), or
 - Member of a group of high risk of exposure such as healthcare workers etc., or
 - Require screening for any other reason, e.g. doctor's orders, hygiene directive etc.
- Participant must be of legal age and must be able to understand the procedure and letter of consent.
- Patient provides written consent prior to enrollment.

Exclusion criteria of individuals

- Persons younger than 18 years old are excluded from the study.
- Pregnant or breastfeeding women are excluded from the study.
- Persons unable to provide written informed consent are excluded.
- Persons with bleeding disorder are excluded from the study as a precaution.
- Persons in institutions where they are (involuntarily) held due to an official order or a court order are excluded from the study.
- Hospitalized patients/inpatients are excluded.
- Application of nasal spray within 15 min prior to testing.
- Participants with symptoms on the day of testing are excluded, if any of their symptoms started more than 7 days prior to testing.
- Asymptomatic participants are excluded, if they experienced any symptoms in the 14 days prior to testing.

Inclusion of Dräger test samples/data

All data is presented and assessed in the study report. Only results with both valid Dräger test and valid PCR results are included in the data set for clinical performance assessment. A Dräger Antigen Test SARS-CoV-2 result is valid when:

- Pouch intact upon visual inspection,
- Desiccant bag present,
- Kit not expired,
- All components (sample collector, test cassette) present,
- Kit appears undamaged and ampoule is intact (no leaking apparent),
- Indicator ring is colored prior to testing,
- Results were read according to this study protocol.

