4.4 Collection of results

The study staff records patient and testing information (mostly by checking boxes) in the respective CRF:

- Age
- Gender
- Any COVID-19 symptoms? If yes, which and since when?

After Dräger Test specimen collection, the participants indicate the pain level of sample collection (none, light, strong, or unbearable), which is recorded in the CRF. Dräger Test results (positive, negative, or invalid) are entered on the corresponding CRF directly after testing. They are not shared with the participants and do not inform any steps regarding patient/participant management. If feasible, the information is also collected electronically.

PCR samples are processed within 72 h of sampling. PCR results are processed according to the Corona Test Center's regular procedures. They include the information of patients and authorities where applicable. If feasible, the information is also collected electronically.

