6.1 Case number estimation

For the case number estimation for the primary endpoint the following assumptions are made:

Sensitivity:

Lindner et al. (in press) collected samples from the anterior nose and observed 27 of 29 SARS-CoV-2 PCR-positive samples ($> 10^6$ copies/mL) to also be rapid antigen test-positive (93.1% agreement). The case number estimation for the Dräger Antigen Test SARS-CoV-2 is based on a more conservative expectation of 90% sensitivity. This assumption is based on preliminary performance data of the test under evaluation and the threshold for PCR set to 10^6 copies/mL (refer to 6.2 for details).

The half width of the confidence interval (W) is pre-determined at 5%, as $90\% \pm 5\%$ provides sufficient test reliability for a daily application in the clinical setting. A test sensitivity of 85% would still meet the PEI criterion for antigen tests (sensitivity $> 80\%$; PEI, 2021).

Specificity:

Lindner et al. (in press) observed a rapid antigen test specificity of 99.6% (95% CL, CI 97.8-100.0%) in anterior nasal swabs. As a result, the investigational product is expected to be 99% specific. For diagnostic applications, a device should deliver a specificity of 99% with a precision of $\pm 1\%$ in order to be of service, e.g. in the screening of symptomatic patient at times of high incidence. It also needs to be taken into account that the intended use of the investigational product is for screening; ultimate confirmation of the preliminary result remains for more sensitive PCR testing.

Separate calculations for case numbers for sensitivity and specificity of the test are performed following the approach by Hajian-Tilaki (2014). The following formulae are used:

$$N(SN) = z^2 \times \frac{(SN(1 - SN))}{W^2 \times P}$$
$$N(SP) = z^2 \times \frac{(SP(1 - SP))}{W^2 \times (1 - P)}$$

with

- N = Case Number
- SN = Sensitivity
- SP = Specificity
- z = z-value corresponding to a confidence level of 95%
- P = Prevalence of disease in the test population. Prevalence is assumed to be at least 20% based on current data from the prospective study sites indicating an actual prevalence among all participants tested for SARS-CoV-2 of 25%.
- W = maximum marginal error (half width of 95% confidence interval) for sensitivity and specificity, respectively

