6.3 Assessment of primary objective

Dräger test and PCR results for all participants are recorded. All valid data pairs (valid Dräger test result, valid PCR result, complete records as defined on pp. 13) from the symptomatic group feed into sensitivity and specificity evaluation of the Dräger test. A contingency table is used to present sensitivity, specificity, and associated confidence intervals (CI at a confidence level of 95%).

Table 7. Assessment of results.

Dräger Antigen Test SARS-CoV-2 result	Reference method RT-PCR result	
	Positive	Negative
Positive	True positive (TP)	False positive (FP)
Negative	False negative (FN)	True negative (TN)

Key parameters to be determined:

$$\text{Sensitivity} = \frac{\text{TP}}{\text{TP} + \text{FN}} \times 100$$

$$\text{Specificity} = \frac{\text{TN}}{\text{FP} + \text{TN}} \times 100$$

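### The plan neither excludes nor visibly records a positive antigen test from earlier in the same episode, so the primary sensitivity may be raised by an unknown amount

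*Combined protocol and SAP*

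**What the plan says.** Recruitment rides on routine testing. Section 2 states that "participants are recruited from people presenting themselves for SARS-CoV-2 testing (pharyngeal swab and PCR) at designated testing locations of the study site", and the synopsis adds that the PCR is not initiated for the sponsor. The case mix is therefore whatever comes to the site.

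Section 4.2 lists the accepted reasons for testing: symptoms on the day, known or suspected exposure, membership of a high-risk group, and finally "Require screening for any other reason, e.g. doctor's orders, hygiene directive etc". For the symptomatic group the synopsis also asks for "Symptoms started 0-7 days prior to testing day". No inclusion or exclusion criterion, in the synopsis or in 4.2, mentions an earlier SARS-CoV-2 test result.

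The participant items listed in 4.4 are age, gender and "Any COVID-19 symptoms? If yes, which and since when". The site reports in 4.5, the fields that section 6 requires for a complete case and the subgroups in 6.4 do not mention an earlier result or the reason for referral either.

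Under 6.3, all valid and complete data pairs "from the symptomatic group feed into sensitivity and specificity evaluation of the Dräger test". Section 6.2 counts as reference-positive only samples at or above 10^6 RNA copies/mL.

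Two statements bear on how an earlier antigen result could arise. Section 1 notes that "Several rapid tests have been developed based on immunochemical detection of viral nucleoprotein". Section 6.1, describing the intended use of the investigational product, says that "ultimate confirmation of the preliminary result remains for more sensitive PCR testing".

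**The concern.** Take a person with a two-day cough and a positive rapid antigen test from the day before, who comes for a confirmatory PCR. Nothing in the written criteria keeps that person out, and with a valid data pair and complete record they enter the primary table. A positive result on another test for the same nucleoprotein has already selected an infection with detectable antigen. Among such people the Dräger test should miss fewer cases than among symptomatic people whose antigen status is unknown.

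The effect runs in one direction. A larger sample does not remove it, and the confidence interval does not show it. It matters because section 10 puts key results into the Instructions for Use, and 6.1 sets sensitivity against an external criterion of more than 80%. Section 6.1 also gives the intended use as screening with PCR afterwards, and a person who already has a positive rapid test is past that step.

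A lesser issue is reading. The documents describe no masking of the operator to the participant's history, and 4.3 scores very weak or broken test lines as positive. An operator who knew of an earlier positive result, antigen or PCR, could be influenced on a borderline strip.

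**Working it through.** **1. The plan's own figures.** Inputs from 6.1: SN = 0.90, W = 0.05, P = 0.20, 95% confidence (z = 1.96).

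N(SN) = z² × SN(1 − SN) / (W² × P) = 1.96² × 0.09 / (0.0025 × 0.20) = 691.5. The plan states 691, and 691 × 1.05 = 725.6 gives its 726. The figures reproduce and are not in dispute. Taking the 20% as the share of reference-positives, the plan rests on 691 × 0.20 = 138 of them.

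**2. Can an earlier positive antigen test enter the primary table?** Set side by side, the sections give this:
- Source: people attending for routine PCR (section 2).
- Entry: symptoms on the day, onset within 7 days (synopsis, 4.2). This alone admits a symptomatic person, so the open-ended last reason in 4.2 is not what lets them in.
- Exclusions: none on an earlier result (synopsis, 4.2).
- Record: none among the listed items (4.4, 4.5, 6).
- Analysis: every valid, complete symptomatic pair (6.3).

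Such a person is therefore eligible and is analysed. Whether any attend is not stated.

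**3. Size if they do.** Let f be their share of reference-positives, s1 the sensitivity in them, and s0 the sensitivity in the remaining reference-positives. Then

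observed sensitivity = (1 − f) × s0 + f × s1, so shift = f × (s1 − s0).

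The documents give neither f nor s1. Assumed: s1 = 98%, f = 10%, 20% or 30%. Values for s0: the plan's expected 90%, and 85%, the lower end of the plan's 90% ± 5%.

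| s0 | f = 10% | f = 20% | f = 30% | Shift (points) |
|---|---|---|---|---|
| 90% | 90.8% | 91.6% | 92.4% | 0.8 to 2.4 |
| 85% | 86.3% | 87.6% | 88.9% | 1.3 to 3.9 |

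Wider assumptions (f from 5% to 30%, s1 from 95% to 100%):
- From 90%: 0.05 × 5 = 0.25 to 0.30 × 10 = 3.0 points.
- From 85%: 0.05 × 10 = 0.5 to 0.30 × 15 = 4.5 points.

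To turn a true 85% into an observed 90%, f must equal 5 / (s1 − 85) with s1 in percent: 5/15 = 33% at s1 = 100%, 5/13 = 38% at 98%, and 5/10 = 50% at 95%.

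**4. Cost of removing them without replacement.** Half-width = 1.96 × √(0.09 / number of reference-positives).

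| f | Reference-positives left | Half-width (points) |
|---|---|---|
| 0 | 138 | 5.0 |
| 5% | 131 | 5.1 |
| 10% | 124 | 5.3 |
| 20% | 111 | 5.6 |

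**The case against.** The strongest reply is that all this is read from silence. Several parts of that reply stand.

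- A reader might infer that section 4.2 deliberately admits people because they already tested positive, and that the sensitivity is in fact partly measured in them. The documents do not support this. The open clause concerns screening, no section says that such people attend the site or are enrolled, and the sentence on PCR confirmation in 6.1 describes the product's intended use, not a referral route.
- A reader might extend the argument to an earlier positive PCR. That does not select for antigen detectability. What remains for these people is possible knowledge of the infection when the strip is read, and that too is unconfirmed.
- A reader might take the target to be undiagnosed people. Section 3.1 speaks only of symptomatic individuals who need testing. The shift above is measured against people without an earlier positive antigen test, which fits the screening use in 6.1 but is not how the objective is worded.
- A reader might conclude that these people could never be identified afterwards. That is not established. Section 4.1 refers to the CRF for details, the form itself is not in the text, and 7.2 describes a patient file at the site linked by participant ID.
- The 10^6 copies/mL threshold already confines the denominator to high viral loads, and 6.4 reports results by ct value and by days since onset.

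The threshold argument limits the effect but does not remove it. The plan still expects 10% misses above the threshold, and the anterior-nasal study cited in 6.1 missed 2 of 29. Those misses are what selection on an earlier antigen result would thin out. The s0 values used in the calculation are themselves sensitivities above the threshold.

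**Conclusion.** The gap is real but conditional. On the text available, a symptomatic person with an antigen-positive result earlier in the episode is eligible, is not flagged by any listed item, and counts in the primary two-by-two table. Inclusion of such people would raise the sensitivity; the documents neither show that it happens nor allow its extent to be estimated.

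Under the stated assumptions (98% sensitivity in these people, shares of 10% to 30%), the shift is modest at the plan's own 90% expectation and larger at 85%, below the planned half-width of 5 points in both cases. Only the upper end of the wider ranges, 4.5 points from 85%, comes close to it. The conclusion assumes that a positive result on one nucleoprotein test makes a positive on another more likely, so that s1 exceeds s0.

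The change is worth making because it is cheap and because, without a record of earlier results, the final report could not readily show that the effect is small.

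**What to change.** - Add a CRF item for the reason for testing and for any earlier SARS-CoV-2 result in the current episode: type of test, result and date. If the full CRF already has it, list it in 4.4.
- In 6.3, keep people with an earlier positive antigen test out of the primary two-by-two table, and report sensitivity with and without them. Excluding them in 4.2 and the synopsis is an alternative, but then the comparison is lost.
- Report people with an earlier positive PCR separately, because their infection may be known when the strip is read.
- Define the current episode in advance.

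The cost is one CRF item, a line or two in 6.3 and somewhat fewer reference-positives for the primary estimate. At a 10% share, precision slips by about 0.3 of a point. If the planned precision is to be kept, the synopsis already allows the recruitment period to be extended.
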